5.6 Protocol Deviations

Planned or unplanned deviations may occur on the part of the participant, the investigator, or study research team. In resolution to a deviation, corrective/preventative actions are to be developed and implemented in a timely manner to avoid subsequent deviations. Protocol deviations will be documented and reported as required and assessed where necessary during analysis. If a control or study intervention is noted to not be in use, or key data are missing from the health record, a reason for noncompliance will be documented. Based on findings from STAYWARM1, reasons for noncompliance are hypothesized to arise from patient condition, and lack of familiarity with the study protocol. Several educational initiatives will be developed prior to study commencement for trauma team members, to avoid protocol deviations during the study period.

6.0 CRITERIA FOR OUTCOME ASSESSMENT

6.1 Primary outcome assessment

1. *Feasibility of Ready-Heat® blanket to increase temperature by at least 1°C at eight hours from arrival to the trauma bay in massively bleeding trauma patients.*
If the study intervention is unable to increase body temperature by at least 1°C in 80% of patients at eight hours from arrival, the study as it is currently designed will not be deemed feasible.
2. *Feasibility of adherence to the application of the Ready-Heat® blanket in patients enrolled in the intervention arm throughout the initial trauma bay resuscitation* Failure to apply and maintain the Ready-Heat® blanket in more than 20% of patients enrolled in the intervention arm throughout the initial trauma bay resuscitation, the study will not be deemed feasible.
3. *Feasibility of adherence to body temperature measurement throughout different phases of care within first eight hours of blanket application.*
Failure to measure body temperature throughout different phases of care (i.e.: ED, CT, OR, IR, ICU) within the first eight hours of blanket application in more than 20% of enrolled patients, the study will not be deemed feasible.

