INVESTIGATIONAL PRODUCT AND PLANNED USE	To evaluate the (1) Feasibility of the Ready-Heat® blanket to increase temperature by at least 1°C at eight hours from arrival to the trauma bay in severely injured trauma patients to whom a massive hemorrhage protocol is activated; (2) Feasibility of adherence to the application of the Ready-Heat® blanket in patients enrolled in the intervention arm throughout the trauma bay resuscitation; (3) Feasibility of adherence to body temperature measurement throughout the different phases of care (i.e.: TB, ED, CT scanner suite, OR, IR suite, ICU) ; (4) Feasibility of maintenance of at least one Ready-Heat® blanket applied throughout the different phases of care (i.e.: TB, ED, CT scanner suite, OR, IR suite, ICU)
STUDY DESIGN	A phase I, single center, pilot, feasibility, prospective, open-label RCT
DURATION OF FOLLOW-UP	From first application of study product to final study visit = 8 hours
TREATMENT ALLOCATIONS	Experimental arm: 2 Ready-Heat® 4-panel blankets Control arm: standard of care (use of warmed blankets and forced air warmed blanket [FAWB])
PATIENT POPULATION	Adults (\geq 16 years old) patients presenting to Sunnybrook Health Sciences Centre (SHSC) as trauma team activations to whom a massive hemorrhage protocol is activated
SETTING	Single academic Level 1 trauma center
PLANNED SAMPLE SIZE	74 patients (37 on each study arm) The anticipated duration for this study's recruitment period is 24 months.
PATIENT INCLUSION/EXCLUSION	
Inclusion criteria:
 
 • Age \geq 16 years • Requires Massive Hemorrhage Protocol activation (see Table 1) in the trauma bay • Admission to the trauma bay between 08:00-20:00hrs on weekdays 
Exclusion criteria:
 
 • Transferred from another healthcare facility • Death in the trauma bay prior to randomization • Arrival to trauma bay with ongoing CPR • Patients with penetrating head injury with Glasgow Coma Scale of 3 AND loss of brain matter through the wound

RANDOMIZATION	Web-based computerized allocation sequence generated by independent statistician

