STUDY OUTCOMES	
Primary outcomes (feasibility):
 
 (1) Feasibility of performing a pilot pragmatic randomized controlled trial (RCT) to evaluate effectiveness of the Ready-Heat® blanket to increase temperature by at least 1°C at eight hours from time of blanket placement in the trauma bay in severely injured trauma patients to whom a massive hemorrhage protocol is activated (2) Feasibility of adherence to the application of the Ready-Heat® blanket in patients enrolled in the intervention arm throughout the trauma bay resuscitation; (3) Feasibility of adherence to body temperature measurement throughout the different phases of care (i.e.: TB, ED, CT scanner suite, OR, IR suite, ICU) within the first eight hours of blanket application. (4) Feasibility of maintenance of at least one blanket applied throughout the different phases of care (i.e.: TB, ED, CT scanner suite, OR, IR suite, ICU) 
Secondary Measures:
 
 (1) Concurrent warming strategies used (i.e.: fluid warmers, FAWB, etc.) within the first eight hours of blanket application in conjunction with or replacement of Ready-Heat® chemical heating blanket; (2) Number of units of blood products (plasma, red blood cells, platelets, fibrinogen concentrate) transfused within 24 hours of trauma bay arrival; (3) Coagulation (platelet count, INR, fibrinogen) and perfusion parameters (pH, base deficit, serum lactate) measured on arrival, and at the next time points collected as per clinician discretion; (4) Hemoglobin level measured on arrival, and at the next time points collected as per clinician discretion. 
Secondary Safety Measures:
 
 (1) Number of times blanket is placed directly on the skin; (2) Skin redness and/or burns.
STATISTICAL ANALYSIS	
The results of this pilot trial will be used to assess the feasibility and inform the design of a definitive trial. We will present point estimates of feasibility outcomes with 95% confidence intervals.
 
Demographic and clinical characteristics will be summarized in total and by two arms using mean, standard deviation (SD), median (interquartiles) and range for continuous variables, and percentages for categorical

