	
variables. The Wilcoxon rank-sum test, Chi-square test or Fisher exact test will be applied for comparing continuous or categorical variables between two arms, as appropriate. The proportion (and 95% confidence intervals) of patients with an increased temperature by at least 1°C at 8 hours from arrival to the trauma bay will be calculated and compared between two arms using Chi-square or Fisher exact test as appropriate. Linear mixed model will be used to search for significant time trends in two arms on the hourly body temperature measurements within the first eight hours of blanket application. To compare coagulation and perfusion parameters measured on arrival and over the first 8 hours, between two arms, linear mixed model will also be performed for the repeated measurements. P-value < 0.05 will be considered statistically significant.

--	---

[figure not shown]

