2.1 Background

2.1.1 Hypothermia and Mortality in Trauma

Massively bleeding hypothermic trauma patients have 2.7-fold higher odds of mortality in the first 24 hours of hospital admission, increased length of stay, and increased need for transfusion.¹⁻⁷ Hypothermia is independently associated with mortality in traumatically injured patients due to its negative physiologic effects on hemostasis, cardiorespiratory and renal function.⁸ Despite this, a retrospective quality review at our institution found that approximately 30% of trauma patients will have hypothermia despite the treatment provided.⁹

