2.1.2 Conventional re-warming strategies for in-hospital patients

The most common first-line active surface rewarming strategies involve the use of a combination of forced air warming blankets (FAWB), and warmed blankets. Unfortunately, these strategies are cumbersome and ineffective,¹⁰ particularly during the initial hours of admission where multiple transfers occur.¹¹ FAWB requires continuous power, which limits portability. In addition, thermally warmed blankets require interchange at frequent intervals.

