3.0 OBJECTIVES AND SCIENTIFIC AIMS

3.1 Study Objectives

1 - To investigate the feasibility of using the Ready-Heat® chemical heating blanket to increase the body temperature by at least 1°C in severely injured trauma patients with activation of a massive hemorrhage protocol (MHP), compared to conventional in-hospital surface rewarming methods (e.g., warmed blankets and/or FAWB) for the first eight hours of blanket application on the patient.

3.2 Primary feasibility outcome:

1 - Feasibility of enrolling the 74 patients over a span of two years.

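### The 6.1 rule that makes the study not feasible unless 80% of intervention patients gain 1°C uses no control reference and no arrival temperature, and it conflicts with 3.2 and 3.4

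*Combined protocol and SAP*

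**What the plan says.** **The rule.** Criterion 1 of section 6.1 concerns failure of the study intervention to achieve a rise of "at least 1°C in 80% of patients at eight hours from arrival, the study as it is currently designed will not be deemed feasible". It gives no control value, no between-arm difference and no condition on arrival temperature. Sections 5.2.1 and 5.2.2 contain no temperature criterion.

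**The status of the 1°C rise.** The sections differ:

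| Place | Treatment of the 1°C rise |
|---|---|
| Synopsis, planned use and primary outcome (1) | feasibility |
| 3.1 | feasibility objective: "to increase the body temperature by at least 1°C in severely injured trauma patients", relative to conventional rewarming |
| 3.2 | absent; the only primary feasibility outcome is "Feasibility of enrolling the 74 patients over a span of two years" |
| 3.4 | efficacy outcome |
| 6.1 | first primary criterion; no enrolment criterion is listed |
| 7.2 | analysed under the primary feasibility objective, by arm, with chi-square or Fisher test |

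**The time origin.** The synopsis primary outcome is "to increase temperature by at least 1°C at eight hours from time of blanket placement in the trauma bay". The synopsis planned use has "Feasibility of the Ready-Heat® blanket to increase temperature by at least 1°C at eight hours from arrival to the trauma bay", and the synopsis analysis text refers to "patients with an increased temperature by at least 1°C at 8 hours from arrival to the trauma bay". Sections 5.1, 6.1 and the 7.2 responder analysis also count from arrival.

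**The temperature model.** The fixed effects in 7.2 are time, arm and their interaction, with a random patient effect. Initial temperature is not listed, although Visit 1 (item 10) collects it.

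**The concern.** A patient who arrives cold has room to gain 1°C, and a patient who arrives near normal has little. Without an entry criterion for temperature, the proportion gaining 1°C reflects the case mix as well as the blanket. A failure under 6.1 could mean that the blanket warms poorly, or that too few enrolled patients could gain 1°C. The rule does not separate the two, and it does not consult the randomised control arm that could help.

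The conflict with 3.2 and 3.4 adds to this. A trial that enrols 74 patients in two years meets its only primary feasibility outcome under 3.2, yet 6.1 could declare it not feasible on an outcome that 3.4 calls efficacy. Since the results are meant to support a larger trial (2.2), the verdict should rest on one agreed outcome that can be interpreted.

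**Working it through.** **1. The plan's own figure.** Section 7.1 plans for a compliance rate of 80% to within 10 points. The exact binomial probability of 40 to 51 successes in 57 at 0.80 is 0.95529, which matches the printed table. Equal arms make this 58, or 29 per arm. Dropout gives 29/0.8 = 36.25, so 37 per arm and 74 in total. The calculation reproduces, but it concerns compliance in about 58 patients, not the 1°C rate in one arm. With 29 patients, the exact probability of lying within 10 points of 80% (21 to 26 successes) is 84.0%. The Wald 95% half-width is 1.96 × √(0.8 × 0.2/29) = 14.6 points; with 37 patients it is 12.9.

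**2. The rule at the margin.** I assume that the observed intervention-arm proportion is compared with 80%. Then 0.8 × 29 = 23.2 requires 24 responders, and 0.8 × 37 = 29.6 requires 30.

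| True rate | P(at least 24 of 29) | P(at least 30 of 37) |
|---|---|---|
| 70% | 9% | 9% |
| 80% | 46% | 53% |
| 85% | 74% | 82% |

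An observed 24/29 has an exact 95% CI of 64% to 94%.

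**3. Arrival temperature, from the documents.** Section 3.3 item 7 describes keeping the blankets in the ICU for up to 8 hours or until 37.5°C. Since 37.5 − 1.0 = 36.5, a patient arriving above 36.5°C reaches that point before gaining 1°C.

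**4. Arrival temperature, an illustration.** Section 2.1.1 reports that "approximately 30% of trauma patients will have hypothermia despite the treatment provided". It covers trauma patients generally and gives no cut-off. Assume that 30% of enrolled patients arrive hypothermic and that all of them respond. The response rate q needed in the rest solves 0.30 + 0.70q = 0.80, so q = 71%. If q were 50%, the overall rate would be 0.30 + 0.35 = 65% and the rule would be met with probability 3.0% (n = 29) or 2.6% (n = 37).

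**5. Sensitivity, all inputs assumed.** Let the arrival SD be s0, the 8 h SD s8, the correlation ρ (0.3 or 0.5) and the slope b = ρ·s8/s0. Let the anchor be the arrival mean from which standard care reaches 36.5°C at 8 h, and let the blanket add 1.0°C. Then the 8 h mean is 36.5 + b(μ0 − anchor) + 1.0, the SD of change is √(s0² + s8² − 2ρ·s0·s8), and p = P(change ≥ 1). At mean arrival μ0 = 36.0°C and n = 37:

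- Low end: SDs 1.0/0.8, ρ = 0.3, anchor 36.0. Mean change is 37.5 − 36.0 = 1.5 and its SD is 1.077, so p = 0.679 and the rule is met with probability 6%.
- High end: SDs 0.7/0.6, ρ = 0.5, anchor 35.0. Here b = 0.429, mean change is 37.93 − 36.0 = 1.93 and its SD is 0.656, so p = 0.922 and the probability is 99%. The modelled mean of 37.93°C lies above the 37.5°C point in 3.3.

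In each setting the probability falls, or stays near 100%, as mean arrival temperature rises. With SDs 1.0/0.8 and anchor 35.5 it goes from 97–99% at 35.0°C to 14–40% at 36.0°C. Only this direction is usable. If gain were unrelated to arrival temperature (slope 1), the dependence would vanish.

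**6. Initial temperature in 7.2.** With an assumed arrival SD of 1°C, the standard error of the chance difference between arms in arrival temperature is √(2/29) = 0.26°C or √(2/37) = 0.23°C. Adjustment would account for this difference.

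**The case against.** A pilot may set whatever progression threshold it likes, and 6.1 speaks of the study as designed, so too few patients able to gain 1°C is a legitimate reason to redesign. Failing one criterion while meeting another is also normal; criteria 2 and 3 of 6.1 work that way. Section 7.2 already supplies the responder proportion by arm with 95% CIs, mean curves by arm and an arm-by-time model, from which a careful reader could work out why the rule failed.

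Much of this stands. It would be wrong to say that the plan makes no control comparison; what is missing is the link from that comparison to the verdict. It remains true that the rule as written does not show what needs redesign, and that 3.2 and 3.4 give the outcome a different status.

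A reader might go further and infer that the rule is bound to fail, or that a useless blanket could pass it because standard care warms cold patients anyway. The documents support neither. They give no arrival-temperature distribution or rewarming rate, and 2.1.2 says of conventional methods that "these strategies are cumbersome and ineffective". A reader might also infer that leaving initial temperature out of the model biases the comparison. Under randomisation it does not; the cost is precision and unadjusted chance imbalance. The plan also does not say whether the arrival reading enters as a time-zero response.

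**Conclusion.** The point holds and should be fixed. It is firm on the text: criterion 1 is an unconditioned single-arm rule, nothing ties the 7.2 comparison to it, 6.1 has no enrolment criterion, and the synopsis, 3.1, 6.1 and 7.2 disagree with 3.2 and 3.4 on whether the 1°C rise is feasibility or efficacy.

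Dependence on arrival temperature is likely, and 3.3 item 7 supports it, but its size cannot be given. The 6% to 99% range shows how far the answer moves with assumed inputs and should not be read as a forecast. The 46% to 53% chance of meeting the rule at a true rate of 80% needs no temperature assumption, only the reading that the observed intervention-arm proportion is compared with 80%. The model point is minor.

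**What to change.** 1. Reconcile 6.1, the synopsis, 3.1 and 7.2 with 3.2 and 3.4 so that the single-arm 1°C response does not decide feasibility alone. Either report it by arm with 95% CI as the 3.4 efficacy outcome, or keep it in 6.1 and read it alongside the between-arm difference with 95% CI and by arrival temperature. The difference has to be read as an estimate, not a test: for an assumed 80% versus 60%, two-sided power at 0.05 is 38% with 29 per arm and 47% with 37.
2. In 7.2, adjust the temperature model for initial temperature, using a reading taken before blanket placement, and report the adjusted 8 h difference between arms with 95% CI.
3. Use one time origin for the 1°C outcome throughout.
4. The sponsor must reconcile the 37.5°C end point in 3.3 with the fixed 8 hours in 5.1 and 5.3.3.5. The control-arm descriptions also need reconciling, because any reading against control depends on them: two warmed blankets only in 5.1, forced air plus two warmed blankets in 5.3.3.4, one warmed blanket in 5.3.3.5.

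The cost is text edits, with no new data and no more patients. The downside is that the responder figure no longer serves as a stand-alone go/no-go criterion. Patients without a pre-blanket reading would need a stated handling rule in the adjusted model.

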7.2 Final Analysis Plan

Demographic and clinical characteristics will be summarized in total and by two arms using mean, SD, median (interquartiles) and range for continuous variables, and percentages for categorical variables. Wilcoxon rank-sum test, Chi-square test or Fisher exact test will be applied for comparing continuous or categorical variables between two arms, as appropriate. To investigate the primary objective on the feasibility of using the Ready-Heat® chemical heating blanket, the proportion (and 95% CIs) of patients with an increased body temperature by at least 1°C at 8 hours from arrival to the trauma bay will be calculated and compared between two arms using Chi-square or Fisher exact test as appropriate. Line graph (with mean and SD) of body temperature over the first 8 hours of blanket application will be plotted for two treatment arms. To search for significant time trends in two arms on the hourly body

temperature measurements within first 8 hours of blanket application, linear mixed effects repeated model will be performed with both fixed (time in hours, treatment arms, and arms by time interaction) and random (patient) effects. To compare treatment effects on the coagulation parameters (platelet count, INR, fibrinogen level), perfusion parameters (pH, base deficit, serum lactate), and hemoglobin levels measured on arrival and over the first 8 hours, linear mixed effects repeated model will also be performed with both fixed and random effects. Skewness and Kurtosis will be tested on the distribution of coagulation, perfusion and hemoglobin parameters. Natural logarithm transformation will be applied to normalize the distribution if necessary. Descriptive analysis will be summarized in total and by arms for safety measurements (i.e., number of units of blood products transfused, number of times blanket is placed directly on patient skin, and number of times patients developed redness and/or skin burns). All analyses will be conducted using Statistical Analysis Software (SAS version 9.4, Cary, NC) and R package (version 4.3.0). P-value < 0.05 will be considered statistically significant.

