3.4 Efficacy Outcomes

9- Increase of temperature from admission up to 8 hours of 1 degree Celsius

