5.4.1 Study Visits

The following information will be collected during study visits either in person or remotely reviewing electronic health records. During weekdays, 8 am to 8 pm, the research assistant will be following the patient across the different phases/locations of care and will be collecting data at the same time. Research assistants will access all documented data on the next weekday. Visits and specific data collection are detailed as follows:

5.4.1.1 Visit 1

On admission to the trauma bay: Demographics, injury characteristics and surgical management:

1. Date of injury
2. Time of injury
3. Sex
4. Age
5. Types of surgical procedures performed in the first 8 hours following hospital arrival
6. Date of arrival
7. Time of arrival
8. Time of randomization
9. Name of attending TTL and sub-TTL (if applicable)
10. Initial temperature recorded
11. Was the blanket placed on the patient? Yes/No
12. Time that the blanket was placed on the patient, if registered
13. Reason why blanket was not applied
14. Blanket applied directly to the patient's skin? Yes/No
15. Use of fluid warmers
16. Use of FAWB

5.4.1.2 Visit 2

Within the first eight hours of blanket application:

1. Location of the patient
2. Is the blanket kept on the patient? (Yes/No)
3. If not, what was the reason it was removed?
4. Temperature recorded, hourly (Yes/No)
5. If yes, the temperature recorded
6. Type of temperature measurement
7. Blanket applied directly to patient's skin? Yes/No
8. Use of FAWB
9. Use of fluid warmers

At discretion of the clinician, within the first eight hours of blanket application:

10. Coagulation (platelet count, INR, fibrinogen)
11. Perfusion parameters (pH, base deficit, serum lactate)
12. Hemoglobin

13. Number of units of red blood cells, plasma, platelets, and fibrinogen concentrate administered within the first 8 hours

5.4.1.3 Visit 3

At 24 hours post blanket application:

1. Number of units of red blood cells, plasma, platelets, and fibrinogen concentrate administered within the first 24 hours
2. Type of injury (blunt/penetrating)
3. Injury Severity Score (ISS)
4. Frequency of safety events with skin

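### The between-arm test for the primary objective cuts the 8-hour temperature change at 1°C, and the plan names no 8-hour difference in °C; under assumptions the documents do not supply, the cut costs that one test about 33% to 46% of its information

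*Combined protocol and SAP*

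**What the plan says.** Section 7.2 opens the relevant sentence with "To investigate the primary objective on the feasibility of using the Ready-Heat® chemical heating blanket". It then names the quantity, a proportion, and its use: "patients with an increased body temperature by at least 1°C at 8 hours from arrival to the trauma bay will be calculated and compared between". The test between the arms is to be Chi-square or Fisher exact. The Protocol Summary says the same of that proportion: it "will be calculated and compared between two arms using Chi-square or Fisher exact test as appropriate".

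The outcome appears in two other roles. Section 3.4 lists it as an efficacy outcome, "Increase of temperature from admission up to 8 hours of 1 degree Celsius". Section 6.1 uses it as a feasibility criterion that begins "If the study intervention is unable to increase body temperature by at least 1°C in 80% of patients at eight hours from arrival".

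The underlying measure is continuous and is collected. In section 5.4.1, Visit 1 asks for "Initial temperature recorded". Visit 2 asks each hour whether a temperature was taken and then "If yes, the temperature recorded".

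Section 7.2 also plans a plot of mean and SD by arm, and a linear mixed model of hourly temperature with time, arm, arm-by-time and a random patient effect. Its stated purpose is to look for time trends in the two arms over 8 hours of blanket application. No contrast at 8 hours, estimate in °C or confidence interval is named for it.

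**The concern.** After the cut, a rise of 0.9°C counts the same as a fall, and a rise of 1.1°C the same as one of 3°C. The documents give no source for 1°C as the scale on which to compare the arms.

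The unadjusted test also ignores where each patient started. Eligibility (section 5.2.1) does not require a low temperature, and section 2.1.1 puts hypothermia at about 30% of trauma patients. A patient who arrives at 36.5°C must reach 37.5°C to count as a responder, so response depends on arrival temperature.

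At stake is what the pilot hands on. Section 7.1 says it should sharpen the sample size of a definitive trial. As planned, the between-arm result tied to the primary objective would be a difference in proportions with a wide interval and a p-value read against 0.05. An adjusted mean difference in °C, from readings already taken, is not promised anywhere.

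**Working it through.** **The plan's own figure.** Section 7.1 sizes the trial for one proportion of 80% to within ±10 points. Exact binomial coverage, P(|p̂ − 0.80| ≤ 0.10), is 0.95529 at N = 57, as printed. At N = 58 it is 0.953. Inflation for dropout gives 29/0.8 = 36.25, so 37 per arm and 74 in total. The plan's figures reproduce, and none concerns a between-arm comparison.

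**Inputs.** From the documents: 80% responders (the section 6.1 threshold, used here as the intervention rate p1), 29 evaluable or 37 enrolled per arm (7.1), and alpha 0.05 (7.2; two-sided assumed). Not in the documents, so assumed: a control rate p0 of 40% to 70%, and normal changes with equal SD.

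**Information kept by the cut.** The standardised mean difference implied by the two rates is d = z(0.80) − z(p0). Relative efficiency is [(p1 − p0)² / (p1q1 + p0q0)] / (d²/2), with q = 1 − p. For p0 = 0.50, d = 0.842, and (0.09/0.41)/(0.842²/2) = 0.2195/0.354 = 0.62.

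**Power.** Fisher and uncorrected Chi-square power come from exact enumeration of two binomials; t-test power comes from the noncentral t with 2n − 2 degrees of freedom. At 29 per arm:

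| Control rate | d | Relative efficiency | Fisher | Chi-square | t-test |
|---|---|---|---|---|---|
| 40% | 1.095 | 0.67 | 83% | 89% | 98% |
| 50% | 0.842 | 0.62 | 57% | 67% | 88% |
| 60% | 0.588 | 0.58 | 28% | 38% | 60% |
| 70% | 0.317 | 0.54 | 8% | 14% | 22% |

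The loss is therefore 1 − 0.67 = 33% to 1 − 0.54 = 46%. The gain over Chi-square is about 8 to 22 points (8.4 at control 70%), and over Fisher 14 to 31. At 37 per arm the figures are 71% / 79% / 95% at control 50% and 38% / 48% / 70% at control 60%. No gain from adjusting for arrival temperature is counted.

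**Width of the planned result.** The 95% half-width of the risk difference at control 50% is 1.96 × √[(0.16 + 0.25)/29] = 0.233. It is 22 to 23 points across the range.

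**Sensitivity of the loss.** Comparing sample sizes for 80% power against the exact t-test gives 30% at control 20% (10 against 7 per arm) and 49% at control 75% (1094 against 563). The small-effect loss under normality is 36% at p = 0.5 and 51% at p = 0.8. Under a logistic shape it is 18% and 47%.

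**Sensitivity of the power gain** (simulation, 29 per arm, Welch t-test against Chi-square):
- Right skew (gamma, shape 4): 73% against 67% at control 50%; 41% against 38% at control 60%.
- Left skew: 93% at control 50% and 72% at control 60%, against the same Chi-square figures.
- Heavy tails (t, 3 df), control 50%: about 64% to 65% against 67%.
- SD 0.8 on intervention and 1.2 on control: 69% against 67% at control 50%; 27% against 38% at control 60%.
- SD 1.2 on intervention and 0.6 on control, control 50%: 98% against 67%.

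The reversal at control 60% has a simple cause. The means lie 0.8 × 0.842 = 0.673 and 1.2 × 0.253 = 0.304 above the cut, a difference of 0.37. With both SDs at 1 it would be 0.588. The same responder rates then imply a smaller shift in means.

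**The case against.** The strongest reply is that the same paragraph of 7.2 already models hourly temperature by arm. A difference at 8 hours is a combination of the fitted arm and arm-by-time terms. A reader might infer that the trial as a whole throws away a third to a half of its temperature information; the documents do not support that. The loss belongs to one test. What remains is that the model is not tied to the primary objective, has no named contrast or interval, and runs from blanket application, while the responder outcome runs from arrival.

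Second, this is a feasibility pilot. Section 3.2 makes enrolment the primary feasibility outcome, 3.4 files the 1°C rise under efficacy, and 7.1 claims no between-arm power. A reader might conclude that the trial is underpowered or its sample size wrong. That does not follow, since no stated figure depends on this test. Yet 7.2 does attach the test to the primary objective and sets a 0.05 threshold, so its efficiency is a fair question.

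Third, section 6.1 needs a binary quantity. That stands, and the proportion should be kept.

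Fourth, the power gain is not guaranteed. That also stands. Equal SD is doubtful where room to rise differs between patients, and the simulations include cases with no gain or a loss. The case for °C rests as much on its use in planning the next trial as on power.

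**Conclusion.** The concern holds in a limited form. The between-arm comparison tied to the primary objective is a test of a dichotomised change, and the plan names no adjusted 8-hour difference in °C to stand beside it. With 80% responding on intervention, 40% to 70% on control, and normal changes of equal SD, the cut costs this test about 33% to 46% of its information and about 8 to 22 points of power against Chi-square at 29 per arm. Every one of those conditions is an assumption. The 80% is a feasibility threshold in the plan, not a predicted response rate. A reader might take 33% to 46% as a property of the plan. It is not: other normal settings give about 30% to 51%, a logistic shape as little as 18%, and some distributions remove or reverse the power gain. The plan's sample size is unaffected.

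**What to change.** In section 7.2 and the matching Summary text:

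- Make the main between-arm temperature comparison the difference in mean temperature at 8 hours, adjusted for arrival temperature, in °C with a 95% CI.
- Take it as a named contrast from the mixed model already planned (arm, time, arm-by-time, random patient effect), with arrival temperature added as a covariate. State whether time enters as a linear term or by hour, because the contrast depends on it. Patients with earlier hourly readings but none at 8 hours still contribute, which a single-time ANCOVA would not allow.
- Use one time origin for this contrast and the responder proportion. At present one runs from blanket application and the other from arrival.
- Keep the proportion with a rise of at least 1°C, by arm with 95% CI, for the section 6.1 criterion. Its Chi-square or Fisher test may stay as secondary.

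The cost is SAP wording and one added covariate and contrast, with no new data or patients. The downside is that the result in °C relies on an additive effect and on readings missing at random. The second assumption is least comfortable for patients who die within the 8 hours, so the text should say how they are handled.
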